8.9 Immunogenicity assessments

Immunogenicity (IG, production of anti-TIN816 antibodies) serum samples will be obtained and evaluated in all participants at all dose levels including the placebo group as defined in the assessment schedule ([Table 1-2](#)). Unscheduled ADA samples may be collected in case of a safety event ([Section 8.4](#)) which is considered to be potentially immunogenicity-related. In case of suspected allergic hypersensitivity, the participant should return to the site and a sample to assess immunogenicity will be collected. Additionally, serum samples should be collected at the final visit from participants who discontinued study treatment or were withdrawn from the study. Details on immunogenicity serum sample collection, numbering, processing and shipment are provided in the Laboratory Manual.

Immunogenicity will be evaluated in serum by a validated three-tiered assay approach. All samples will be screened for potential anti-TIN816 antibodies. Any positive screen result is confirmed using a confirmatory assay where sample screening signal suppression upon addition of drug in excess is investigated. If a sample is confirmed positive for the presence of anti-TIN816 antibodies it will be further analyzed using a titration assay.

8.10 Health economics OR Medical resource utilization and health economics

Health economics OR Medical resource utilization and health economics parameters are not evaluated in this study.

9 Statistical considerations

9.1 Analysis sets

The Randomized Analysis Set (RAS) consists of all randomized participants. This analysis set will not be used for any analyses and is solely intended for providing complete information on how participants were randomized.

The PK analysis set will include all participants who survive Day 7 with at least one available valid (i.e., not flagged for exclusion) PK concentration measurement, who received complete study drug regardless of infusion duration.

The PD analysis set will include all participants with available PD data. Participants will be analyzed according to actual study treatment received.

The full analysis set (FAS) comprises all participants to whom study treatment has been assigned by randomization. According to the intent to treat principle, participants will be analyzed according to the treatment they have been assigned to during the randomization procedure. Mis-randomized participants, that is, participants who were randomized incorrectly

and did not receive any study drug will be excluded from this set. This will be the analysis set used for all efficacy analyses.

The safety set (SAF) includes all participants who received one dose of study treatment. Participants will be analyzed according to the study treatment received, where treatment received is defined as the participant took at least one dose of that study treatment regardless treatment group randomized to. This will be the analysis set used for safety analysis except for PK/PD analysis.

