Visit Numbers ¹	1	100			110	120	130	140	150	160	170	180	190	200
Days	-2 to -1	1			2	3	5	8	11	14	21	30	60	90
Time (post-dose)	-	pre-dose ³	0H	2 H (END of the infusion) ³	-	-	-	-	-	-	-	-	-	-
Urine volume (6 +/1 hours or 24 hours collection) ¹¹		X			X	X	X	X	X	X	X	X	X	X
Creatinine clearance		X			X	X	X	X	X	X	X	X	X	X
APACHE II Score		X												
Concomitant medications	X	X			X	X	X	X	X	X	X	X	X	X
Surgical and Medical Procedures	X	X		X	X	X	X	X	X	X	X	X	X	X
Adverse Events	X	X		X	X	X	X	X	X	X	X	X	X	X
Serious Adverse Events	X	X		X	X	X	X	X	X	X	X	X	X	X
Disposition	X	X												X
Study completion information ¹²														X

^X Assessment to be recorded in the clinical database or received electronically from a vendor

¹ Visit structure given for internal programming purpose only

² Day 1 = baseline values and treatment

³ Two samples will be collected on Day 1, one sample pre-dose and one sample (post-infusion) immediately after or within 15 minutes after the two hour study drug infusion

⁴ At Day 1, vital signs will be monitored before and after study drug infusion, and data will be collected at the following timepoints: a) immediately before the administration of the study drug, and b) immediately after the completion of the administration of the study drug, which includes post-dose saline flushing.

⁵ Pregnancy test to be performed locally and more frequently if required by local regulations.

⁶ Scheduled assessments (Clinical Chemistry, Hematology, Urinalysis, Coagulation parameters, Hepatitis screen) as well as follow-up safety labs to be analyzed by

Period	Screening	Treatment		Post-treatment Visits									
				Day 2	Day 3	Day 5	Day 8	Day 11	Day 14	Day 21	Day 30	Day 60	Day 90/End of Study (EOS)
Visit Name	Screening	Day 1 ²		110	120	130	140	150	160	170	180	190	200
Visit Numbers ¹	1	100		2	3	5	8	11	14	21	30	60	90
Days	-2 to -1	1		-	-	-	-	-	-	-	-	-	-
Time (post-dose)	-	pre-dose ³	0H	2 H (END of the infusion) ³		-	-	-	-	-	-	-	-

local laboratory and results entered in the eCRF

7 Sample will be shipped and analyzed by the sponsor designated laboratory.
[REDACTED]

9 During hospitalization, one midpoint serum creatinine sample will be collected during the 6 hour +/-1 urine collection. When participants are discharged from the hospital, one serum creatinine sample will be collected at the end of the 24 hour urine collection period. Dedicated blood samples for serum creatinine and Cystatin C will be analyzed by the central laboratory.

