8.7 Pharmacokinetics

PK serum samples will be collected at the time points defined in the Assessment Schedule ([Table 1-2](#)). Two samples will be collected on Day 1: one sample pre-dose and one sample post-dose within 15 minutes at the end of the two hour study drug infusion. In addition, PK samples should be collected at additional days as indicated in [Table 1-2](#), optimally always at that time point of the day when study drug administration started on Day 1 (e.g. Day 2 sample should be taken 24 h after starting TIN816/placebo infusion).

Instructions regarding sample collection, numbering, processing and shipment are outlined in the Laboratory Manual. The exact time of treatment administration, sample number and time of sample collection are recorded for each sample collected in the eCRF. Sampling problems are to be documented in the eCRF and may include but are not limited to hemolyzed or lipemic samples, insufficient sample volumes, and/or a lack of sample collections.

Pharmacokinetic (PK) samples will be evaluated in all participants treated with TIN816.

TIN816 concentrations will be determined in serum by a validated ligand binding assay with a lower limit of quantification (LLOQ) of approximately 10 ng/mL. The detailed method description of analysis will be given in the method validation report. Concentrations below the LLOQ will be reported as “zero” and missing data will be labeled as such in the Bioanalytical Data Report. Values below the LLOQ will be treated as zero for calculation of PK parameters as well as for summary statistics.

For standard pharmacokinetic abbreviations and definitions refer to Appendix 2 ([Section 10.2](#)) of this protocol. The following pharmacokinetic parameters will be determined from the serum concentration time data using the actual recorded sampling times and non-compartmental method(s) with Phoenix WinNonlin (Version 6.4 or higher): C_{max} , T_{max} , AUC_{last} , AUC_{inf} , $T_{1/2}$, V_z , Cl , and other relevant PK parameters (data permitting).

[figure not shown]

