9.3.1 Definition of primary endpoint(s)

The primary endpoint is all PK related parameters (Table 9-1). The analyses will be performed on PK population set.

TIN816 serum concentration data will be listed by treatment, participant and visit/sampling time point. Descriptive summary statistics of TIN816 serum concentration data will be provided by treatment, and visit/sampling time point, including the frequency of concentrations below the LLOQ and reported as zero.

Summary statistics will include mean (arithmetic and geometric), Standard Deviation (SD), CV (arithmetic and geometric), median, minimum and maximum. An exception to this is T_{max} where median, minimum, and maximum will be presented. PK data will also be represented graphically (including spaghetti plots, boxplots and mean plots with SD) by treatment arm, participant and visit.

Drug concentrations below LLOQ will be treated as missing for the calculation of the geometric means and geometric CV%, and as zero for all other calculations including calculation of PK parameters. Pharmacokinetic parameters will be calculated as described in [Section 8.7](#) and will be listed by treatment and participant and summarized by treatment with descriptive statistics as listed below.

The pharmacokinetic parameters listed in the table below will be determined from the serum concentration time data using the actual recorded sampling times and non-compartmental method(s) with Phoenix WinNonlin (Version 6.4 or higher). Other relevant PK parameters may be added (data permitting).

Table 9-1 Non-compartmental pharmacokinetic parameters

PK parameter	Definition
AUC_{last}	The AUC from time zero to the last measurable concentration sampling time (t_{last}) (mass \times time \times volume $^{-1}$)
AUC_{inf}	The AUC from time zero to infinity (mass \times time \times volume $^{-1}$)
C_{max}	The maximum (peak) observed serum drug concentration after single dose administration (mass \times volume $^{-1}$)

T_{max}	The time to reach maximum (peak) serum drug concentration after single dose administration (time)
$T_{1/2}$	The elimination half-life associated with the terminal slope (λz) of a semi logarithmic concentration-time curve (time). Use qualifier for other half-lives
Cl	The total body clearance of drug from the serum following intravenous administration (volume \times time $^{-1}$)
V_z	The apparent volume of distribution during terminal phase following intravenous administration (associated with λz) (volume)

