9.3.4 Handling of missing values not related to intercurrent event

Missing primary endpoint values due to protocol deviations or other issues related to a pandemic are not anticipated as measures have been put in place, where possible, to allow for the protocol assessments to be conducted. In case missing values do occur for such reasons, only data available will be used.

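### No rule says when Cmax, Tmax and AUClast are evaluable, so a missed end-of-infusion sample would put a 24-hour or later concentration into the Cmax summary

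*Protocol*

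**What the plan says.** **Who enters the set.** Protocol 9.1 sets three conditions. "The PK analysis set will include all participants who survive Day 7", each must have "at least one available valid (i.e., not flagged for exclusion) PK concentration measurement", and the set is limited to those "who received complete study drug regardless of infusion duration". SAP 2.2 repeats this and adds that treatment was received. The valid concentration may come from any time point, and no rule for flagging concentrations is given. SAP 5.2.1 adds that no protocol deviation removes a participant from an analysis set.

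**When samples are taken.** Protocol 8.7 schedules for Day 1 "one sample pre-dose and one sample post-dose within 15 minutes at the end of the two hour study drug infusion"; footnote 3 of Table 1-2 agrees. The next draw is on Day 2: "Day 2 sample should be taken 24 h after starting TIN816/placebo infusion". Later draws are on Days 3, 5, 8, 14, 30, 60 and 90 (protocol 4.1).

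**How parameters are derived.** Table 9-1 defines Cmax as "The maximum (peak) observed serum drug concentration after single dose administration". Protocol 8.7 uses the linear trapezoidal rule from the start of infusion, and counts values below the quantification limit as zero. Its only evaluability rule concerns the terminal phase: at least three points after Cmax and an adjusted R² of at least 0.75. If half-life cannot be calculated, AUCinf, Vz and CL are not reported and AUClast is used. For missing primary endpoint values due to protocol deviations or pandemic-related issues, protocol 9.3.4 says: "In case missing values do occur for such reasons, only data available will be used".

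**The concern.** One draw in a 15-minute window carries all the information on the peak. Protocol 8.7 itself expects sampling problems, naming haemolysed samples, insufficient volume and samples not collected. When that draw fails, the definition of Cmax does not return a missing value. It returns the largest concentration that remains, from 24 hours or later, and Tmax follows it. The first AUC segment then joins zero at the start of infusion to the 24-hour value. A participant who misses only this sample can still satisfy the terminal-phase rule, so nothing in the plan catches the profile.

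Cmax is a primary parameter and, with AUCinf, one of the two on which the sample size rests. At the interim look about 8 participants, so about 6 on TIN816 at 3:1 allocation, are compared with healthy volunteers to decide whether the study continues unmodified. No numerical criterion for similarity is given. A peak that is low because it was sampled late could be read as an effect of sepsis.

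**Working it through.** **Inputs from the documents.** n = 15 on TIN816, GCV 0.25, two-sided 95% interval (protocol 9.9.1; SAP 3.1); sampling at 0, 2 and 24 h, then Days 3, 5, 8 and 14, that is 48, 96, 168 and 312 h after the start of infusion.

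**Assumptions.** Let r be the ratio of the 24-hour to the end-of-infusion concentration, and k the number of missed end-of-infusion samples. Neither is given. One-compartment decline over the 22 hours between the two samples gives r = exp(−ln 2 × 22/(24 × half-life in days)): 0.81 at 3 days, 0.91 at 7 days and 0.95 at 13 days. An early distribution phase would lower r; 0.6 illustrates this.

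**1. The plan's own figure.** CI factor = exp(t(0.975, n−1) × √ln(1+GCV²)/√n). At n = 15 and GCV 0.25: exp(2.145 × √0.0606/√15) = 1.146, which meets the stated 15% margin. The same formula gives 1.299 and 1.448 at GCV 0.50 and 0.75, against 1.31 and 1.47 in the table. Those two rows match n = 14 (1.314 and 1.471), a small difference that does not affect this point.

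**2. Geometric mean Cmax.** Each affected participant's Cmax is multiplied by r, so the geometric mean changes by r^(k/n) − 1.

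| Missed | r = 0.95 | r = 0.81 | r = 0.6 |
|---|---|---|---|
| 1 of 15 | −0.3% | −1.4% | −3.3% |
| 2 of 15 | −0.7% | −2.8% | −6.6% |
| 3 of 15 | −1.0% | −4.1% | −9.7% |
| 1 of 6 (interim) | −0.9% | −3.5% | −8.2% |

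**3. Spread and precision, 2 of 15 missed.** Log variance = ln(1+0.25²) + p(1−p)(ln r)², with p = 2/15.
- r = 0.6: 0.0606 + 0.1156 × 0.261 = 0.0908. GCV = √(e^0.0908 − 1) = 0.31. CI factor = exp(2.145 × √(0.0908/15)) = 1.18.
- r = 0.81: variance 0.0658, GCV 0.26, factor 1.153.
- r = 0.95: factor 1.146, unchanged to three decimals.

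**4. AUC of the affected participant.** With end-of-infusion concentration C, the trapezoid over 0–24 h is C(1 + 11(1+r)) = C(12 + 11r). Without the 2-hour sample it is 12rC. The loss is C(12 − r), in concentration × hours. Over all samples to Day 14, with C = 1:

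| Half-life | With 2-h sample | Without | Shortfall |
|---|---|---|---|
| 3 days | 103.5 | 92.3 | 11% |
| 7 days | 178.0 | 166.9 | 6% |
| 13 days | 226.0 | 214.9 | 5% |

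The same absolute loss enters AUClast and AUCinf. CL is dose divided by AUCinf, so it is biased upwards, and Vz with it.

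**The case against.** **Stronger readings that a reader might infer.**
- That the set admits anyone with one concentration. It does not: Day 7 survival and the complete dose are also required. Serum concentrations are themselves a primary endpoint, so one valid value is a reasonable entry threshold. The gap lies in the parameter rules, not in the set definition.
- That AUC is halved. Only the first-day segment shrinks that far. Its retained share is 12r/(12 + 11r), or 50% at r = 0.92 and 39% at r = 0.6. First-day AUC is not a reported parameter; the documents list AUClast and AUCinf, and the SAP adds AUC0-14d.
- That the 15% margin is lost. At 2 of 15 missed this is clear at r = 0.6 (1.18) but marginal at r = 0.81 (1.153), and it does not occur at r = 0.95. The documents' indirect hints, attenuation of purinergic signalling for roughly three weeks (protocol 4.3) and detectability for at least 38 days (protocol 6.7), fit slow elimination. They do not exclude an early distribution phase.

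**Other points against.** The draw follows a supervised infusion, with vital signs, an ECG and close observation around its end, so misses may be few. Protocol 9.3.4 does not order a 24-hour value to be reported as Cmax, and SAP 5.2.1 bars exclusion from sets, not omission of one parameter. Individual listings, spaghetti plots and the range of Tmax would expose a 24-hour Tmax; the estimand also uses the median; and the analysis is descriptive.

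**What stands.** These limit the size and make detection likely, but no rule says what to do once the problem is seen. The definition of Cmax by itself still puts the late value into the summary. Deciding case by case, in a sponsor team with unblinded data, is what a rule fixed in advance avoids.

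**Conclusion.** The gap is real and worth closing, and it is modest in most scenarios. Under the stated rules a complete-dose Day 7 survivor without a valid end-of-infusion sample contributes a wrong Cmax and Tmax, where a missing value would be correct, and an AUC that is too low.

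With 2 of 15 missed, geometric mean Cmax is about 1–3% low at r = 0.95–0.81 and 6.6% low at r = 0.6. In the last case GCV rises from 0.25 to 0.31 and the CI factor from 1.146 to 1.18. With 1 of about 6 missed at the interim look, the fall is about 1–4% and 8%. For the affected participant, AUC to the Day 14 sample is about 5–11% low at half-lives of 13–3 days under one-compartment decline.

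The direction follows from the documents whenever concentrations fall between the end of infusion and 24 hours. The sizes rest on assumed values of r, half-life and the number of missed samples.

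**What to change.** Before the interim look, add to protocol 8.7 and 9.3.1 and to SAP 2.5.1:

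1. Cmax and Tmax (and Cmax/D in the SAP) are set to missing in the summaries when no valid sample lies within a fixed tolerance of the actual end of infusion. State the tolerance.
2. The profile is still listed. Its valid later concentrations stay in the by-time summaries, and its half-life is kept. Since the terminal-phase rule counts points after Cmax, say how they are counted when Cmax is missing.
3. AUClast, AUCinf and AUC0-14d, with the derived CL and Vz, are flagged and summarised with and without flagged participants. Dropping AUCs that may be only a few percent low would waste data.
4. The number evaluable is shown for each parameter.

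The PK set definition can stay as it is.

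**Cost.** Wording, and one extra summary for the flagged parameters. n for Cmax and Tmax may be slightly lower: at GCV 0.25 the CI factor is 1.153 at n = 14 and 1.160 at n = 13, so the 15% margin is itself slightly exceeded. That is a small, visible loss of precision in exchange for a Cmax summary free of mis-timed peaks.

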9.2 Statistical analyses

9.2.1 General considerations

This study is to investigate PK, safety, tolerability and efficacy. There is no inferential analysis to be performed. The analyses will be mainly based on descriptive statistics.

Categorical data will be presented as frequencies and percentages, including quartiles. For continuous data, mean, standard deviation, median, minimum, and maximum will be presented. For PK parameters, n, mean, median, minimum, maximum, coefficient of variation (CV (%)) to mean, geometric mean, and CV(%) to geometric mean will be presented.

The baseline visit is defined at Day 1 unless specified. Parameters that are not collected at Day 1, the screening visit will be used as baseline.

For hospital-acquired AKI, a stable serum creatinine obtained in the hospital prior to AKI will be used as reference baseline: otherwise, a baseline serum creatinine is defined in the following order of preference:

1. Median value within 3 months of the hospital admission. If not available:
2. Median value between 3 and 6 months prior to hospital admission. If not available:
3. At hospital admission.

The study will exclude participants whose AKI diagnosis or AKI presence based on investigator's clinical judgement has a period longer than 48 hours prior to study drug administration because of the criticality of an early treatment for patients with SA-AKI.

9.2.2 Participant demographics and other baseline characteristics

Demographic and other baseline data including disease characteristics will be summarized descriptively for all participants and by treatment group.

Relevant medical histories and current medical conditions at baseline will be summarized separately by system organ class and preferred term, for all participants and by treatment group.

9.2.3 Treatments

The Safety set will be used for the analyses below. Categorical data will be summarized as frequencies and percentages. For continuous data, mean, standard deviation, median, 25th and 75th percentiles, minimum, and maximum will be presented. Descriptive statistics will be provided.

Concomitant medications and significant non-drug therapies prior to and after the start of the study treatment will be listed and summarized according to the anatomical therapeutic chemical (ATC) classification system by treatment group.

9.3 Primary endpoint(s)/estimand(s) analysis

The primary endpoint is all TIN816 concentrations in serum PK parameters, including C_{max} , T_{max} , $T_{1/2}$, Cl , V_z , AUC_{last} and AUC_{inf} . It will be summarized descriptively for participants with at least one dose of study treatment.

There is no inferential analysis to be performed.

9.3.1 Definition of primary endpoint(s)

The primary endpoint is all PK related parameters (Table 9-1). The analyses will be performed on PK population set.

TIN816 serum concentration data will be listed by treatment, participant and visit/sampling time point. Descriptive summary statistics of TIN816 serum concentration data will be provided by treatment, and visit/sampling time point, including the frequency of concentrations below the LLOQ and reported as zero.

Summary statistics will include mean (arithmetic and geometric), Standard Deviation (SD), CV (arithmetic and geometric), median, minimum and maximum. An exception to this is T_{max} where median, minimum, and maximum will be presented. PK data will also be represented graphically (including spaghetti plots, boxplots and mean plots with SD) by treatment arm, participant and visit.

Drug concentrations below LLOQ will be treated as missing for the calculation of the geometric means and geometric CV%, and as zero for all other calculations including calculation of PK parameters. Pharmacokinetic parameters will be calculated as described in [Section 8.7](#) and will be listed by treatment and participant and summarized by treatment with descriptive statistics as listed below.

The pharmacokinetic parameters listed in the table below will be determined from the serum concentration time data using the actual recorded sampling times and non-compartmental method(s) with Phoenix WinNonlin (Version 6.4 or higher). Other relevant PK parameters may be added (data permitting).

Table 9-1 Non-compartmental pharmacokinetic parameters

PK parameter	Definition
AUC_{last}	The AUC from time zero to the last measurable concentration sampling time (t_{last}) (mass \times time \times volume $^{-1}$)
AUC_{inf}	The AUC from time zero to infinity (mass \times time \times volume $^{-1}$)
C_{max}	The maximum (peak) observed serum drug concentration after single dose administration (mass \times volume $^{-1}$)

T_{max}	The time to reach maximum (peak) serum drug concentration after single dose administration (time)
$T_{1/2}$	The elimination half-life associated with the terminal slope (λz) of a semi logarithmic concentration-time curve (time). Use qualifier for other half-lives
Cl	The total body clearance of drug from the serum following intravenous administration (volume \times time $^{-1}$)
V_z	The apparent volume of distribution during terminal phase following intravenous administration (associated with λz) (volume)

